3.2 Sample Size

The present trial is a pharmacodynamic comparison of a marketed product to a new formulation of the same. With 188 subjects per treatment group, the trial has at least 85% power to demonstrate the non-inferiority of MENOPUR liquid to MENOPUR powder in the number of fertilized oocytes at the 1-sided significance level of 0.025. This is based on the results for MENOPUR powder from the COMBINE trial (data on file) conducted in a similar setting (GnRH agonist protocol, MENOPUR starting dose of 225 IU for the first five days, insemination by ICSI etc.) and in a similar population (infertile women between 18 and 42 years). The mean (SD) of the number of fertilized oocytes were 7.88 (5.15) with similar results in the two age groups (7.92 in the <35 years age group vs. 7.80 in

the \geq 35 years age group). The non-inferiority margin of -1.60 will retain 80% of the expected comparator effect.

After adjusting for 5% missing data, approximately 400 subjects will be randomized (1:1) into this trial, stratified by trial site and age (<35 years and \geq 35 years).

A blinded sample size reassessment will be done when data on the primary endpoint are available for 70% of the planned subjects or when 300 subjects are randomized, whichever comes first. The sample size reassessment will be done without breaking the blind and without inflating the type I error of the trial, in line with current regulatory guidelines. The expected maximum number of subjects to be randomized is 500 (250 subjects per treatment group), corresponding to a blinded one-sample (both groups pooled) standard deviation estimate of 5.8 and 85% power.

4 Subject Disposition

All subjects screened will be accounted for. The number of subjects screened but not randomized to treatment will be presented with the reason for screen failure.

Subject disposition with respect to each analysis set will be tabulated. The number of subjects in the intention-to-treat (ITT) analysis set will be used as the denominator when calculating percentages. Randomized subjects, randomized subjects treated with investigational medicinal product (IMP; MENOPUR liquid including Placebo to MENOPUR powder or MENOPUR powder including Placebo to MENOPUR liquid), and randomized subjects prematurely discontinued from the trial will be summarized. Randomized subjects prematurely discontinued from the trial will have the reason for premature discontinuation summarized.

Subject disposition with respect to the start of the COVID-19 pandemic trial hold will be tabulated and listed using the ITT analysis set. Subject disposition will be summarized by whether a subject had exited the trial before or after the start of the COVID-19 pandemic trial hold. Of the subjects that had not yet exited the trial, the subject status (i.e.; not yet recruited, in screening, or randomized) will be summarized.

Subjects that were in screening but had not yet been randomized prior to the COVID-19 pandemic trial hold were considered screen failures. Subjects that were screen failed due to the COVID-19 pandemic trial hold could re-enter the trial, beginning again the screening process. All subjects that were screen failed due to the COVID-19 pandemic trial hold will be listed along with an indicator of whether the subject re-entered the trial or not. Those subjects that re-entered the trial will have two screening identification numbers. Both identification numbers will be included in the listing.

For subjects that were already randomized but had not yet exited the trial at the start of the COVID-19 pandemic trial hold, the last visit completed prior to the trial hold will be summarized.

A detailed listing of selected trial assessments will be created. Included will be an indicator of whether the corresponding visit took place, an indicator of whether the visit was expected to occur before, during, or after the COVID-19 pandemic trial hold, and an indicator of whether the missingness was due to the COVID-19 pandemic.

5 **Protocol Deviations**

The rating of protocol deviations as 'minor' and 'major', as well as the criteria for major protocol deviations with the implication of exclusions from the per-protocol (PP) analysis set will be decided on the basis of a blinded review of data before declaration of clean file and lock of database.

The list of major protocol deviations will be detailed and documented in the clean file document prior to database release. Major protocol deviations will be summarized and listed by subject.

Major protocol deviations, such as significant non-compliance with the IMP regimen, NIMP regimens, or other serious unforeseen deviations that may affect the conclusions for the primary endpoint of the trial, will lead to exclusion of data from the PP analysis set. Other protocol deviations will not lead to the exclusion from the PP analysis set.

Protocol deviations due to COVID-19 will be listed.

6 Analysis sets

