where m_i and se_i are the estimated mean treatment difference and standard error for the treatment difference from the *i*th complete dataset and m_{MI} and se_{MI} are the pooled estimates. The mean difference in the number of 2PN between the MENOPUR liquid and the MENOPUR powder groups will be estimated as m_{MI} and the associated 95% confidence interval will be calculated as $m_{MI} \pm 1.96 * se_{MI}$.

The fourth sensitivity analysis will again repeat the primary endpoint analysis using the mITT analysis set but will instead use a 95.08% two-sided confidence interval to assess non-inferiority. This sensitivity analysis assesses the impact of any Type I error inflation incurred due to performing a blinded sample size recalculation during a non-inferiority study. See Appendix 1 for more details.

Ferring Pharmaceuticals

Furthermore, the number of fertilized oocytes will be summarized for several subgroups:

- By reason for infertility
- By center
- By number of oocytes retrieved (<4, 4-7, 8-14, 15-19, and ≥20)
- By AMH level on stimulation day 1 (<7.5, 7.5-<15, 15-<25, ≥25 pmol/L; ≤ median, > median)

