11.3 Neonatal Health

The gestational age, gender, weight, length, and Apgar scores (1 minute, 5 minutes, and 10 minutes) will be presented by treatment group. Furthermore, admissions to care units (NICU, NCU, or PCU), admissions to care units for longer than 2 hours, malformations or congenital anomalies, neonatal death, and important medical events will be presented by treatment group at birth, at 4 weeks after live birth, and after 6 months following live birth.

Neonatal SAEs will be summarized from birth through a minimum of 6 months after birth. Written narratives will be issued for all SAEs.

Parameters relating to maternal health will also be presented by treatment group. These will include clinically relevant pregnancy, labor, or delivery complications, COVID-19 infection, exposure to risk factors of congenital anomalies or malformations, and maternal death in connection with pregnancy or labor.

12 Interim analyses

A sample size reassessment will be performed without breaking the blind and without meaningful inflation of the Type I error of the trial (see Appendix 1), in line with the current regulatory guidelines for non-inferiority trials by the Food and Drug Administration (FDA). The one-sample standard deviation of the primary efficacy endpoint will be evaluated in a blinded manner in relation to the assumptions underlying the sample size calculation.

The sample size reassessment is to take place when 70% of the planned sample size has provided a primary endpoint (280 primary endpoints) or when 300 subjects have been randomized, whichever occurs first.

A restricted recalculation rule for the sample size reassessment will be used. The trial will originally target 400 randomized subjects. At the time of the interim analysis, the estimated one-sample standard deviation will be used to recalculate the required sample size. If the recalculated sample size is less than 400, then the targeted sample size will remain at 400 (i.e.; the sample size will never decrease below 400). If the recalculated sample size is greater than 400, however, then the targeted sample size will be increased to either the recalculated sample size or 500, whichever is smaller.

13 Deviations from the protocol

There is one deviation from the planned analysis in the protocol. Center will be incorporated into statistical analyses as a fixed effect instead of a random effect.

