Because randomization is stratified by age strata and center, it was planned in the protocol to perform analyses by adjusting for both age strata and center. Age strata was to be incorporated as a fixed effect and center was to be incorporated as a random effect.

In this statistical analysis plan, however, we incorporate center as a fixed effect. The reason for doing so is twofold. First, centers are rarely chosen at random. Second, the interpretation of an interaction between center and any other variable of interest would be complicated by the use of a random effect. Interactions between fixed effects are much more readily interpretable. While there are no pre-planned analyses that incorporate an interaction that includes center, it is possible that a post-hoc analysis could.

14 Tables, Listings and Figures

Tables, listings, and figures (TLF) will be presented in a separate document.

15 References

1. Rubin, D.B. (1987) Multiple imputation for nonresponse in surveys. New York: John Wiley & Sons.

Appendix 1

Assessment of Type I Error Inflation

In November 2019, the FDA released a guidance for industry document titled, "Adaptive Designs for Clinical Trials of Drugs and Biologics." Of relevance for the present trial, Section IV: Adaptive Designs Based on Non-Comparative Data states, "These adaptations generally do not inflate the Type I error probability. However, there is the potential for limited Type I error probability inflation in trials incorporating hypothesis tests of non-inferiority or equivalence (Friede and Kieser 2003). Sponsors should evaluate the extent of inflation in these scenarios." The present trial is a non-inferiority study that includes a form of non-comparative adaptive design, namely a blinded sample size recalculation.

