Using the methods described in Appendix 1 of Friede and Kieser (2003), a simulation study was performed. The simulation study assessed the potential Type I error of the present trial given the design considerations for the sample size recalculation (See Section 3.2). The 'true' pooled standard deviation was set to range from 3.0 to 15.0 using increments of 0.1. For each increment, 10,000,000 simulations were performed. Based upon the design considerations of the present trial, the minimum sample size was set to 400, the maximum sample size was set to 500, and the sample size recruited at the time of the sample size recalculation was set to 280. Likewise, when recalculating the sample size during each simulation rep, an alternative treatment difference of 0 was assumed, the non-inferiority margin was set to -1.6, a two-sided alpha of 0.05 was used, and the power was set to 85%.

The results of the simulation can be seen in Figure 0-1 below. For true pooled standard deviations that are less than 5 and greater than 6, the Type I error is well controlled. For true pooled standard deviations between 5 and 6, there is a small amount of Type I error inflation. The maximum Type I error observed was 0.0253705, which occurred at a true pooled standard deviation of 5.6.

Figure 0-1: Actual Type I error of the 000303 trial given the true pooled standard deviation.

One conservative method for controlling the maximum Type I error inflation was illustrated by Friede and Stammer (2010). An iterative procedure is performed, adjusting alpha until the maximum observed Type I error is within a certain distance, epsilon, of the predefined desirable level of Type I error. This method was applied to the present trial by setting epsilon equal to 0.0001 (i.e.; a maximum Type I error no greater than 0.0251).

The results of applying the procedure can be seen in Figure 0-2 below. When adjusting the onesided Type I error from 0.025 to 0.0246 (or, equivalently, the two-sided Type I error from 0.05 to 0.0492), the maximum observed Type I error is within 0.0001 of the pre-specified Type I error of 0.025. The maximum observed Type I error was 0.0250291 and again occurred at a standard deviation of 5.6.

Figure 0-2: Adjusted Type I error after applying an alpha correction.

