The Type I error inflation observed in Figure 0-1 is considered to be small and inconsequential. Therefore, no adjustments to the primary analysis are taken. A sensitivity analysis, however, is added. As described in Section 9.2.2, the primary analysis will be repeated using the same analysis set and imputation approach, but a different alpha level when constructing the two-sided confidence interval. Instead of a two-sided 95% confidence interval, a two-sided 95.08% confidence interval will be constructed. This confidence interval reflects the adjustment necessary to contain the maximum Type I error to be within 0.0001 of the pre-specified desired level of Type I error.

Below are the references made in the appendix.

- 1. Friede, T. & Kieser, M. (2003) Blinded sample size reassessment in non-inferiority and equivalence trials. *Statistics in Medicine*, 22:995-1007. DOI: 10.102/sim.1456.
- 2. Friede, T. & Stammer, H. (2010) Blinded sample size recalculation in noninferiority trials: A case study in dermatology. *Drug Information Journal*, 44:598-608.

Ferring Pharmaceuticals

Appendix 2

Variable Code	Variable	Units	Low	High
RBC	Erythocytes	10^12/L	< 3.0	N.A
WBC	Leukocytes	10^9/L	< 2.5	> 15.0
HGB	Haemoglobin	g/L	< 100	> 190
НСТ	Haematocrit	RATIO	< 0.28	> 0.5
EOSLE	Eosinophils/Leukocytes	%	N.A	≥ 10
NEUTLE	Neutrophils/Leukocytes	%	≤15	≥ 90
LYMLE	Lymphocytes/Leukocytes	%	≤10	≥ 80
MONOLE	Monocytes/Leukocytes	%	N.A	≥20
BASOLE	Basophils	%	N.A	≥ 5
PLAT	Platelets	10^9/L	< 110	> 600
AST	AST	IU/L	N.A	> 3xULN
BUN	Blood urea nitrogen	mmol/L	N.A	> 12.5
CA	Calcium	mmol/L	< 1.75	> 2.74
CL	Chloride	mmol/L	N.A	N.A
ALT	ALT	IU/L	N.A	> 3xULN
CREAT	Creatinine	umol/L	N.A	> 3xULN
GGT	GGT	IU/L	N.A	> 3xULN
GLUC	Glucose	mmol/L	< 2.5	> 16.7
K	Potassium	mmol/L	< 3.0	> 5.8
SODIUM	Sodium	mmol/L	< 125	> 155
ALP	Alkaline phosphatase	IU/L	N.A	$> 3 \mathrm{xULN}$
LH	Luteinizing hormone	IU/L	N.A	>10

Table 1Markedly Abnormal Criteria for Laboratory Tests

Table 2	Markedly	Abnormal	Criteria	for V	Vital Signs	*
1 a 0 10 2	wiarkeury	Automat	Cincina	101	v nai oigiid	,

Variable	Criterion Value	Change from Baseline
Systolic blood pressure	\geq 180 mmHg \leq 90 mmHg	Increase of $\ge 20 \text{ mmHg}$ Decrease of $\ge 20 \text{ mmHg}$
Diastolic blood pressure	\geq 105 mmHg \leq 50 mmHg	Increase of ≥ 15 mmHg Decrease of ≥ 15 mmHg
Pulse	≥ 120 bpm ≤ 50 bpm	Increase of ≥ 15 bpm Decrease of ≥ 15 bpm

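### Does the SAP's statement that the blinded sample size reassessment does not inflate the type I error need correcting, given that its Appendix 1 shows a small excess?

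*SAP*

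**What the plan says.** SAP 3.2 says the reassessment is done "without breaking the blind and without inflating the type I error of the trial". The same words stand in the protocol synopsis and protocol 9.1, and protocol 9.9 makes the same claim.

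SAP 12, which sets out the recalculation rule, says instead "without meaningful inflation of the Type I error of the trial (see Appendix 1".

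SAP Appendix 1 quotes FDA guidance of November 2019, according to which "there is the potential for limited Type I error probability inflation in trials incorporating hypothesis tests of non-inferiority or equivalence", and reports the simulation made in response:

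- "For true pooled standard deviations between 5 and 6, there is a small amount of Type I error inflation".
- Below an SD of 5 and above 6 the error is described as well controlled.
- On the size of the peak, it states: "The maximum Type I error observed was 0.0253705, which occurred at a true pooled standard deviation of 5.6".
- Its judgement is that "The Type I error inflation observed in Figure 0-1 is considered to be small and inconsequential", so the primary analysis is not adjusted.

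SAP 9.2.2 adds a fourth sensitivity analysis, which "will instead use a 95.08% two-sided confidence interval to assess non-inferiority".

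SAP 13 opens with "There is one deviation from the planned analysis in the protocol"; that deviation is center as a fixed rather than a random effect.

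**The concern.** A confirmatory non-inferiority trial depends on its type I error. Here the sample size section states an unqualified property that an appendix to the same document contradicts. Appendix 1 also sends the reader to Section 3.2 for the design considerations, and 3.2 contains no pointer back. The SD range is not remote: the planning SD (5.15) and the SD that matches the cap of 500 subjects (5.8) both lie in the 5 to 6 band where the SAP reports inflation, and the primary 95% interval is unadjusted. A reader who saw only 3.2 could carry the absolute claim into the trial report. SAP 13 does not mention that the protocol's statement has been softened.

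**Working it through.** **Inputs (SAP 3.2, 12 and Appendix 1).** One-sided alpha 0.025; power 85%; margin 1.60; planning SD 5.15; 5% missing data; 280 subjects at the reassessment; total N restricted to 400–500; 10,000,000 repetitions per SD.

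**1. The design figures.** Total N = 4·SD²·(1.960 + 1.036)² / 1.6².

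- SD 5.15: N ≈ 372, or 187 per group (SAP: 188). 376 / 0.95 = 396, in line with about 400.
- SD 5.8: N ≈ 472, or 236 per group. 472 / 0.95 = 497, in line with 500.

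**2. Is the reported excess simulation noise?** Monte Carlo SE = √(0.025 × 0.975 / 10,000,000) = 0.000049. (0.0253705 − 0.025) / 0.000049 ≈ 7.5. It is not noise.

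**3. Independent simulation.** Normal data, true difference −1.6, blinded one-sample variance at 280 subjects, N from the formula above restricted to 400–500, final two-sample t-test. The recalculated N was taken both without and with division by 0.95 for missing data.

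| True SD | One-sided alpha | Without allowance | With allowance | Repetitions |
|---|---|---|---|---|
| 5.15 | 0.025 | 0.02504 | 0.02513 | 8 million |
| 5.6 | 0.025 | 0.02536 | 0.02531 | 30 million |
| 5.8 | 0.025 | 0.02528 | 0.02526 | 8 million |
| 6.3 | 0.025 | 0.02498 | 0.02500 | 8 million |
| 7.0 | 0.025 | 0.02496 | 0.02506 | 8 million |
| 5.6 | 0.0246 | 0.02491 | 0.02491 | 30 million |

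The Monte Carlo SE is about 0.000055 for 8 million repetitions and 0.00003 for 30 million. The SAP's maximum is reproduced to four decimals (0.0254) without the allowance. The pattern is as expected. At a difference of −1.6 the one-sample variance exceeds SD² by about 1.6² / 4 = 0.64. At SD 5.6 it is therefore about 31.36 + 0.64 = 32.0, giving N ≈ 449, near the middle of 400–500, where the interim data influence N most. Far below or above that, N sits at one of its limits and the inflation disappears.

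**4. Size.** Absolute excess: 0.0253705 − 0.025 = 0.00037. Relative excess: 0.00037 / 0.025 = 1.5%.

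**5. What the 95.08% interval changes.** 1 − 2 × 0.0246 = 0.9508. The normal quantile moves from 1.9600 to 1.9669, a difference of 0.0069.

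- 200 per group, SD 5.15: SE = 5.15 × √(2/200) = 0.515, so the lower limit moves by 0.0069 × 0.515 ≈ 0.004. With t quantiles the half-widths are 1.0125 and 1.0160.
- 237.5 per group (500 less 5%), SD 5.8: SE = 5.8 × √(2/237.5) = 0.532, so it again moves by about 0.004.

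The two intervals can disagree on non-inferiority only if the 95% lower limit falls within about 0.004 oocytes above −1.60.

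**6. Does anything computed depend on the phrase in 3.2?** The primary decision uses the 95% interval and −1.60 in both protocol 9.6.2 and SAP 9.2.1. The floor of 400 and cap of 500 are the same in protocol 9.9 and SAP 12. None of these refers to the phrase.

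**The case for a change.** The strongest case for a correction is that the contradiction is plain on the page, the inflation is demonstrated, it falls in the SD range the trial expects, and the remedy is a single phrase borrowed from SAP 12. The sentence in 3.2 also claims to follow regulatory guidelines, while the guidance quoted in Appendix 1 warns of exactly this effect. All of that is accurate, and 3.2 would read better if it matched SAP 12.

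What does not stand is the step from there to a needed change. The phrase goes back to a protocol dated 14 October 2019. The guidance came out in November 2019, and the SAP (version 2.0, August 2021) carried out the evaluation it asks for and published the result. Nothing is hidden from a reader of the SAP.

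The point about SAP 13 fails too. Its opening sentence concerns the planned analysis, and on this matter the planned analysis is unchanged. A more exact description of an operating characteristic, with a sensitivity analysis added, is not a deviation from it.

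Making the 95.08% interval primary would bring the error at SD 5.6 down to about 0.0249. (The SAP's own 0.0250291 is only about 0.6 Monte Carlo SE above 0.025, so it is no argument against that option.) But it would change the protocol-specified test to remove an excess of 0.00037, and it would lower power from 85.1% to 84.9% with 237.5 per group at SD 5.8. The sponsor weighed this openly and kept 95%, which is a fair trade-off.

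**Conclusion.** The mismatch is a clerical slip: SAP 3.2 kept the protocol's unqualified words, while SAP 12 and Appendix 1 state the position correctly. The true excess in one-sided type I error is at most about 0.0004. It is disclosed and quantified, and the 95.08% sensitivity analysis covers it; that interval could alter the conclusion only within about 0.004 oocytes of the margin. Aligning the wording would change no test, sample size, result or conclusion, so no change to the plan follows.

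This rests on simulations with normal data and a two-sample t-test. The endpoint is a count, and the actual analysis is an ANOVA with age strata and center. The match with the SAP's figure shows that its calculation is right under those conditions; the effect of skewness or of center on the error rate was not examined here.

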6.1 Intention-to-Treat Analysis Set

The intention-to-treat (ITT) analysis set comprises of all randomized (as planned) subjects.

6.2 Modified Intention-to-Treat Analysis Set

The modified intention-to-treat (mITT) analysis set comprises all randomized (as planned) subjects who received at least 1 dose of IMP (MENOPUR liquid including Placebo to MENOPUR powder or MENOPUR powder including Placebo to MENOPUR liquid).

6.3 Per Protocol Analysis Set

The per protocol (PP) analysis set comprises all mITT subjects except those excluded as a result of major protocol deviations.

6.4 Safety Analysis Set

The safety analysis set comprises all treated subjects and is analyzed according to the actual treatment received.

7 Trial Population

7.1 Display of Trial Population Characteristics

Descriptive statistics of demographics and other baseline characteristics will be presented by treatment group as detailed in Section 1.2.1 for the subjects in the mITT, PP, and Safety analysis sets, unless otherwise noted. In the case that the Safety analysis set is identical to the mITT analysis set, presentations will use the mITT and PP analysis sets. Summaries will be made using all subjects, subjects in the <35 years age strata, and subject in the \geq 35 years age strata.

In the case of multiple assessments prior to the first exposure to IMP, the baseline value is defined as described in Section 1.1.1.

All demographic and baseline characteristics will also be presented in listings. Listings will be produced for the mITT analysis set only.

Unless otherwise noted, missing data will not be imputed.

